7.2 Subjects and Sites Numbers

This study will be conducted only on patients with a regular indication for JTIN as per IFU (no off-label use will be included): the nail is indicated for fractures, osteotomies, malunions and non-unions in femur and tibia in pediatric patients suffering from osteogenesis imperfecta. The JTIN is intended to be used in pediatric patients, older than 18 months.

This study includes only one site (monocentric) located in Paris, France. The site was chosen for this study due to the number of subject devices already implanted, and the wideness of the indications covered by the surgeries. The site was also positively evaluated by sponsor for the appropriate qualification and competency of the investigator and of the staff, and availability of facilities and equipment.

The enrollment objective for this study is of 20 evaluable cases (i.e. procedures, see paragraph "Determination of the Sample Size"). For the purposes of this study, a case is defined as one implanted JTIN nail in one treated bone. Each case can be evaluated and recorded from implantation to the last visit for this study (see "Visits and Assessments Schedule" table and "Procedure" paragraph) or up to implant removal if this happens before the last visit. For each case one eCRF record will be created (see "Subject Identifier" paragraph).

Therefore, a single patient at the clinical site can contribute for more than one case e.g.: a patient can have several JTIN each implanted in a different bone, or can have more JTIN implanted in the same bone but at different times.

7.3 Study duration

The study duration at the site is planned for 1,5 years (18 months), that includes the enrollment period of 6 months plus 1 year of data collection up to last patient last visit.

The study duration for each subject implant is approximately 1 year from the date of surgery, according to the visit schedule. Since the subjects will follow standard clinical care of the site

and due to the observational character of the study, the study duration for each subject can be slightly different according to the standard of care.

7.4 Measures to Minimize or Avoid Bias

7.4.1 Blinding and Randomization

The present observational study is an un-controlled, single arm and open-label study therefore, no pre-defined subgroups are planned for the enrolled patients and no stratification, nor randomization, nor blinding procedures will be used.

7.4.2 Subject Identifier

Each time a patient is planned to be treated with JTIN (or has been treated with JTIN after the 1st of January 2022, i.e. retrospectively), he/she is considered potentially eligible for the study and will be screened by the clinical site team to check if they satisfy all inclusion and exclusion criteria. Only if they satisfy the criteria, they will be informed about the study and asked if they want to participate. Patients' non-opposition to the participation to the study and data collection of the single specific implantation of JTIN will be duly documented in medical records. After non-opposition documentation the site staff will create a record in the eCRF that generates a consecutive identification number (ID), related to the procedure. The ID will be registered in the patient log. If the same patient agrees to participate for another JTIN procedure: another ID will be created and a reference to the first ID is made in the dedicated field in the eCRF and in the patient log.

7.5 End of Study (EOS)

The sponsor has the right to close this observational study at any time.
The study will be terminated prematurely in the following cases:

- If the enrolment rate and data collection are significantly delayed;
- If the sponsor will be informed that the activities related to the study are conducted in conflict with the present protocol;
- Any other reason for the sponsor to deem that the prosecution of the study will harm the subjects' health or rights.

8. SELECTION AND WITHDRAWAL OF SUBJECTS

8.1 Subject Inclusion Criteria

A patient will be included in the study if:

- is in pediatric age (> 18 month and < 18 years) at the time of surgery;
- is skeletally immature;
- has a diagnosis for OI;
- has a regular indication for surgical intervention with JTIN to treat femoral and/or tibial fractures, osteotomies, malunions and non-unions;
- Patient and/or legal representative is duly informed and doesn't oppose to participation.

8.2 Subject Exclusion Criteria

A patient will not be included in the study who:

- has a medical condition that is a contraindication according to the manufacturer's instruction for use;
- has any conditions that in the Investigator's opinion may interfere with the study execution or due to which the patient should not participate for safety reasons;
- requires the application of, or has already in-situ the application of concomitant devices that cannot be safely removed (except for permitted concomitant devices paragraph);
- is participating in other clinical trials or has taken part in any clinical study in the last 3 months with exception of analytical trials on genetics study related to OI (i.e. studies that do not include an investigational treatment for the patient such as new drugs or other medical devices);
- is likely to be lost to follow up, according to investigator's opinion.

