OBJECTIVES	
Primary objective: to evaluate the safety of the JTIN, in terms of percentage of procedures with at least one serious/not serious adverse event certainly or possibly related to JTIN up to 1 year follow-up.
 
Secondary objectives: to evaluate clinical safety and performance of the JTIN, in terms of: implant survival for safety, bone union achievement and fracture-free survival for performance.
 
Exploratory objective: The Gillette Functional Assessment Questionnaire will be collected at different times to evaluate the changes after treatment.
								
TYPE OF THE INVESTIGATION	This study on JTIN device is a post-market, prospective and retrospective, observational, single-center study, namely a PMCF study. The design will contain a single arm, will be open label and will not involve randomization nor any additional procedure compared to routine practice.								
PLANNED INVESTIGATION PERIOD	
 
 First patient First visit	Q3 2023	Last patient First visit	Q3 2023	Last patient Last visit	Q4 2024	
 
	First patient First visit	Q3 2023	Last patient First visit	Q3 2023	Last patient Last visit	Q4 2024		
First patient First visit	Q3 2023	Last patient First visit	Q3 2023	Last patient Last visit	Q4 2024				
STUDY DURATION PER SUBJECT	The Study initiation for the subject is to be intended after patient's information and non-opposition (that can be also after the JTIN application surgery). The subject will be treated by the means of JTIN application and will follow standard clinical care of the selected site. If the information and non-opposition occur after the JTIN surgery, previous data will be collected retrospectively. The data from the standard care will be collected for this study up to 1 year follow-up visit.								
CENTER(S) / COUNTRY(IES)	
 
 Hospital	Country (EU)	City	Principal Investigator	
 
 1	France	Paris	[name]	
 
	Hospital	Country (EU)	City	Principal Investigator	1	France	Paris	[name]
Hospital	Country (EU)	City	Principal Investigator						
1	France	Paris	[name]						

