10. STUDY PROCEDURES

10.1 Description of Procedures

Throughout the pre-study meetings, it was assessed and confirmed that the clinical data collected for the study purpose are part of the standard clinical practice for the participating investigational site. As this is an observational study, there are no change or influence on the normal clinical practice of the investigator and patients, and no interference with the local hospital standard of care guidelines and/or the internal therapeutic protocols set and established at the investigational site.

For the purpose of the study, the investigators will screen both:

- patients that have undergone JTIN implantation surgery from the 1st of January 2022
- patients that will receive JTIN implantation surgery (prospectively enrolled);

The investigators shall collect clinical data from the medical record of the subjects, concerning the screening criteria, the surgery (MD application) and 5 following visits: hospital discharge, plaster or immobilization removal, bone consolidation assessment and two follow-up visits. Data from patients' observation are gathered according to the site practice, therefore timelines and visit frequency presented in this protocol are estimated as average of the site normal clinical practice, actual visit timing for each patient will be performed according to investigators and hospital staff evaluation. The subjects will not undergo additional visit nor non-invasive, invasive or burdensome procedures additional to those performed under the normal clinical practice.

The patients' data will be systematically collected by the investigator in the eCRF provided by Sponsor.

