12.3 Determination of the Sample Size

Due to the observational nature of the study, no formal sample size calculation has been done, but a revision of the literature on the complication rates (intended as at least one serious/not serious adverse event certainly or possibly related to the procedure up to 1 year follow-up) has been made. The scientific literature reports that the percentage of procedures which develop at least one serious/not serious adverse event certainly or possibly related to the procedure itself is between 9% and 60%, with a mean of 31%. Assuming a complication rate aligned or better than the mean observed in literature (31%), a sample size of 15 procedures will be sufficient to estimate the adverse event rate with the upper limit of the 95% confidence interval equal or lower than the worst complication rate seen in literature (i.e. 60%).

Starting from this sample size, to also assume that the success rate (intended as proportion of procedures that result in a bone union achieved) is aligned or better than the mean observed in literature (80%), 20 procedures will be needed.

Considering a drop-out or a non-evaluable rate of 20% of the procedures, a total of approximately 25 procedures should be made. Each subject could have from 1 to 4 procedures. Assuming the worst scenario of no more than 1 procedure for subjects, a maximum of 25 subjects needs to be enrolled. Anyway, the enrolment will stop when the total number of the procedures is reached.

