3. *requires the application of, or has already in-situ the application of concomitant devices that cannot be safely removed (except for permitted concomitant devices paragraph);* This criteria cannot be verified with the variables included in the CRF.

4. *is participating in other clinical trials or has taken part in any clinical study in the last 3 months with exception of analytical trials on genetics study related to OI (i.e. studies that do not include an investigational treatment for the patient such as new drugs or other medical devices);* This criteria cannot be verified with the variables included in the CRF.
5. *is likely to be lost to follow up, according to investigator's opinion.* This criteria cannot be verified with the variables included in the CRF.

A list of patients belonging to each of the populations will be sent to the sponsor for confirmation prior to analysis.

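### The opinion-based exclusion for likely loss to follow-up also covers retrospective procedures whose follow-up is partly or wholly known at screening, so the plan permits selection on observed follow-up or outcome

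*Protocol*

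**What the plan says.** Protocol 10.1 draws cases from two sources: patients still to be operated on, and "patients that have undergone JTIN implantation surgery from the 1st of January 2022". Section 7.4.2 handles them together. A patient planned for the nail ("or has been treated with JTIN after the 1st of January 2022, i.e. retrospectively") "will be screened by the clinical site team to check if they satisfy all inclusion and exclusion criteria". The synopsis confirms that enrolment may follow the operation: "If the information and non-opposition occur after the JTIN surgery, previous data will be collected retrospectively".

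The single list in Protocol 8.2, repeated in SAP 12, contains two exclusions that rest on opinion. Exclusion 5 removes a patient who "is likely to be lost to follow up, according to investigator's opinion". Exclusion 2 removes one who "has any conditions that in the Investigator's opinion may interfere with the study execution". Neither is limited to planned surgeries or to what was known at the time of surgery.

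Protocol 12.3 targets about 25 procedures and says that "the enrolment will stop when the total number of the procedures is reached". No section says in what order retrospective patients are approached. Of exclusion 5, SAP 13 says: "This criteria cannot be verified with the variables included in the CRF". SAP 15.1 summarises the patients included and why any of them falls outside an analysis population; it plans no table of treated patients who were screened and left out. Protocol 14.2 provides for full source data verification of the eligibility criteria. Protocol 6.1 states the primary objective for a representative population.

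**The concern.** A forecast of loss to follow-up makes sense before surgery. For a procedure already performed, the investigator holds the medical record and can see who returned and what happened in the meantime. Where a year has passed, the criterion no longer forecasts anything; it is a judgement on known attendance, made by someone who may also know the outcome. A patient removed at that point is a screening failure without an eCRF record, because the record is created only after non-opposition is documented (Protocol 7.4.2).

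At stake is whether the roughly 25 procedures represent the site's experience with the nail. The primary result is a simple percentage of procedures with a related adverse event. Protocol 6.2 has the secondary results compared visually with other devices. Both uses depend on knowing how cases entered the set.

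**Working it through.** **1. The plan's own figures.** Evaluable target 20 and allowance 20% (Protocol 12.3): 20 / (1 − 0.20) = 25, as stated. The figure of 15 for the adverse event rate also reproduces: at an observed 31%, the upper two-sided 95% Clopper-Pearson limit is 60.5% for n = 14 and 59.4% for n = 15, against the 60% ceiling. Neither figure bears on who is selected.

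**2. How many eligible procedures have a completed year.** Inputs: earliest surgery 1 January 2022; first patient Q3 2023 (synopsis); enrolment 6 months and follow-up about 1 year (Protocol 7.3). Assumption, not in the documents: a constant surgery rate.

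- Months from first eligible surgery to start of enrolment: 18 (start of Q3) to 21 (end of Q3).
- Eligible window including enrolment: 18 + 6 = 24 to 21 + 6 = 27 months.
- Performed before enrolment opens: 18/24 = 75% to 21/27 = 78%.
- Of these, already 1 year past surgery: (18 − 12)/24 = 6/24 = 25% to (21 − 12)/27 = 9/27 = 33%.
- If all screening waited until the window closed: 12/24 = 50% to 15/27 = 56%.

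The 25–33% share is the relevant one for a fully known follow-up at the planned start. The other procedures in the 75–78% have part of their year still to run. The synopsis also puts the last patient's first visit in Q3 2023; a window shorter than 6 months would raise these shares.

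**3. What one omitted case does to the primary percentage (illustration; counts assumed).** Start from 8 event procedures in 25.

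| Event cases omitted | Result | Change from previous row |
|---|---|---|
| 0 | 8/25 = 32.0% | – |
| 1 | 7/24 = 29.2% | −2.8 |
| 2 | 6/23 = 26.1% | −3.1 |
| 3 | 5/22 = 22.7% | −3.4 |

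Omitting one event-free case moves it the other way: 8/24 = 33.3%, or +1.3 points. For scale, the 95% Clopper-Pearson interval for 8/25 is 14.9% to 53.5%.

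**4. Direction under the SAP's own rules.** SAP 24.1 contrasts exit because the nail was removed with every other exit reason, and SAP 22 lists loss to follow-up separately. A lost case therefore counts as a surviving implant. SAP 13 puts all JTIN applications in enrolled subjects into the implant set and SAP 14 imputes nothing, so a lost case with no recorded event stays in the denominator as event-free. With assumed counts:

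- Adverse events: 6/20 = 30% without lost cases; adding 5 lost, event-free cases gives 6/25 = 24%.
- Implant survival: 18/20 = 90% without them; 23/25 = 92% with them.

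Keeping such cases out would thus raise the event rate and lower survival, the reverse of what omitting event cases does in step 3. For bone union, the effect depends on whether loss comes before the consolidation visit and on which of the two percentage columns in SAP 14 is read.

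**The case against.** The strongest reply has four parts.

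First, exclusion 5 concerns attendance, not outcome. A child with a complication is not for that reason likely to stop attending, and Protocol 7.2 treats a case followed up to implant removal as properly recorded. This stands as a limit: the criterion selects on outcome only so far as attendance and outcome go together, or the opinion is swayed by what is in the record.

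Second, safeguards exist. Every treated patient is to be screened, and eligibility is fully source-verified. SAP 13 says only that CRF variables cannot verify the criterion, and says the same of 7 of the 10 criteria; it does not say that no check is possible. That is fair. But verification can confirm that an opinion was recorded, not that it was formed independently of the known course, and universal screening comes before the exclusion acts.

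Third, for procedures still within their first year the criterion keeps some predictive meaning. This also stands, and is why 25–33% describes the sharpest part of the problem better than 75–78%.

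Fourth, SAP 3 cites a protocol version dated 02082024 and CRF versions of November 2024, after the planned enrolment period, so new eligibility wording may come too late. That affects which parts of the remedy still work, not whether the gap exists.

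A reader might go further and infer that the plan biases the adverse event rate down and union and survival up. The documents do not support that: step 4 shows effects in the opposite direction. A reader might also take the remark in Protocol 5.2 about patients already treated successfully as a rule to enrol successes only. The criteria in 8.1 and 8.2 contain no such condition, and 7.4.2 has every treated patient screened.

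**Conclusion.** The point holds as a statement of what the plan permits. Followed exactly, the rules let exclusion 5, and likewise exclusion 2, be applied to retrospective procedures with part or all of the follow-up year already known. The target count, the lack of an approach order and the planned disposition summary leave the effect invisible in the report. The documents do not show that selection on outcome took place, and the direction of any bias is not fixed for the adverse event rate, bone union or implant survival.

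The gap is most serious for the 25–33% or so of eligible procedures with a completed year at a Q3 2023 start. That range rests on a constant surgery rate and a 6-month window. About 3 points per omitted event case is an illustration from assumed counts, not an estimate of bias. It is small beside the sampling interval, but the interval does not allow for selection. The study is descriptive with no success threshold, so this is a cheap improvement rather than a flaw that undoes the design.

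**What to change.** 1. **Protocol 8.2 and SAP 12.** State that, for procedures performed before non-opposition was documented, exclusion 5 and any other exclusion resting on the investigator's opinion may not be based on information that arose after surgery.
2. **Protocol 7.4.2.** State that retrospective procedures are included consecutively by surgery date from 1 January 2022, subject to documented non-opposition.
3. **SAP 15.1.** Add a table of all JTIN implants at the site since that date, with the reason for each non-inclusion. This shows whether selection occurred and in which direction, and stays useful if enrolment is already closed.
4. **SAP 23.1 and 24.1.** Report the adverse event and implant-survival percentages also among procedures with 1-year follow-up or an earlier event, so that lost cases are not silently counted as event-free or surviving.

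The cost is some wording, one extra table and one extra denominator. No visit, procedure or treatment changes. The downside is that more cases with incomplete follow-up may enter. The 20% allowance was set with exclusion 5 in force and covers 5 of 25 procedures; a sixth loss would leave 19 evaluable against the target of 20, so the allowance may be used up or exceeded. Some children who have left the centre will remain outside the study because non-opposition cannot be documented; the table in item 3 would at least count them.

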8.3 Subject Withdrawal

Premature discontinuation from the study will occur when an enrolled patient (namely a patient who doesn't oppose to participation) will not undergo the final follow-up visit.

At any time patients may prematurely discontinue from this study for any reason, without explanation and without losing the right to future medical care. The participation of the patient may, at any moment, be terminated by the Investigator as well, if considered appropriate (i.e. the early termination is in the patient's best medical interest).

Patients who prematurely terminate the study are considered as "withdrawal" ("drop out") patients. Possible reasons for withdrawal of a patient from the study are:

- lack of adequate therapeutic response resulting in an unacceptable risk;
- major protocol violation;
- an inclusion or exclusion criteria that becomes invalid;
- serious or intolerable AE preventing the patient from continuing the study;

- refusal of the patient to continue the treatment and/or protocol procedures;
- decision by the Investigator if it would not be in the best interest of the patient to continue the study;
- lost to follow-up;
- death of the patient.

It is understood by all concerned that an excessive rate of withdrawals can render the study not interpretable, therefore, withdrawals of patients should be carefully assessed. However, if a patient decides to withdraw for any reason, all efforts will be made to complete and report the observations as thoroughly as possible in the patient's records and with an end-of-study visit page that will be available in the electronic Case Report Form (eCRF).

Any subject withdrawal, including lost to follow-up, must be traced by the investigator in the patient medical file and in the eCRF, including the possible reasons.

Until such time that the enrolment period is officially closed by the Sponsor, any withdrawn patients may be replaced by recruitment in accordance with the aforementioned protocol to reach the planned number of evaluable cases. The screening number assigned to the withdrawn patient will not be reassigned to another patient.

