6. STUDY OBJECTIVES

6.1 Primary Objective

The primary objective of the study is to evaluate the clinical safety profile of JTIN within the scope of its intended purpose, when used according to the manufacturer IFU on a representative population of subjects and users.

To fulfill this objective, one safety endpoint will be evaluated:

- Percentage (%) of procedures with at least one serious/not serious adverse event certainly or possibly related to JTIN up to 1 year follow-up.

The primary endpoint is used to calculate the sample size of the study.

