9.2.2 Contraindications according to Manufacturer IFU

The JTIN system must not be used if a surgical candidate exhibits or is predisposed to any of the following contraindications:

- Active or suspected latent infections in or near the surgical area
- Compromised bone stock, potentially leading to inadequate or unstable fixation of the device
- Suspected or documented metal sensitivity reactions
- Sepsis
- Mental or physiological conditions, who are unwilling or incapable of following postoperative care instructions as it could result in a treatment failure in the intended population

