22 STUDY EXIT VISIT

This analysis will be performed on FAIS population.

The categorical variables to be described are, N and (%):

- Reason for study exit
 - Subject completed protocol last visit
 - Nail removed
 - Subject does not meet inclusion criteria (a list will be shown)
 - Subject withdrew consent
 - Subject withdrawn by Investigator (a list will be shown)
 - Subject Death
 - Lost to follow-up
 - Subject had an AE that does not permit the continuation of the study (specify nr. of AE: a list will be shown)
 - Other Reason (a list will be shown)

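### Recording of a case stops at nail removal by rule and may stop at other complications, although the charts could supply safety data to 1 year

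*Protocol*

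**What the plan says.** The primary endpoint (Protocol 6.1) is "Percentage (%) of procedures with at least one serious/not serious adverse event certainly or possibly related to JTIN up to 1 year follow-up". Implant survival and fracture-free survival have the same 1-year horizon (6.2), and the Synopsis says data are collected to 1 year from surgery. The study is non-interventional, and investigators take the data from medical records (7.1, 10.1).

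Three sets of text end observation earlier:

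- **Nail removal.** Protocol 7.2 follows a case to the last visit "or up to implant removal if this happens before the last visit". SAP 22 lists nail removal as a reason for study exit.
- **Withdrawal.** Protocol 8.3 opens its list with "Possible reasons for withdrawal of a patient from the study are". The list includes inadequate therapeutic response, major protocol violation, "serious or intolerable AE preventing the patient from continuing the study" and "an inclusion or exclusion criteria that becomes invalid". SAP 22 has a matching exit reason: "Subject had an AE that does not permit the continuation of the study".
- **Selection criteria.** Protocol 8.2 excludes a patient who "has a medical condition that is a contraindication according to the manufacturer's instruction for use". The contraindications in 9.2.2 include "Active or suspected latent infections in or near the surgical area" and, separately, sepsis. Deep infection is also on the list of expected device effects in 11.1.5.

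Protocol 8.3 asks for every effort to complete the observations, with an end-of-study page, when a patient chooses to withdraw. It allows withdrawn patients to be replaced while enrolment is open.

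**The concern.** A chart-based safety study has little reason to stop extracting data when a complication occurs, because the child normally remains in care and the record continues. Where exit is linked to a complication, the follow-up that is lost belongs to the cases of most interest. That loss is informative, and data that were not extracted cannot be recovered in the analysis.

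The protocol itself asks for information that arises after removal. Its definition of a certain causal relationship (11.1.7) looks to what happens once the device is withdrawn. Event resolution must be recorded (11.1.10). Re-operation or revision is a safety variable (12.1.2.2). If recording ends at removal, the later course of an infection, a later fracture of that bone or a further operation on it is outside the dataset, unless the bone receives another JTIN that is enrolled as a new case.

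**Working it through.** **The plan's own figures.** Protocol 12.3 takes a 31% complication rate and 15 procedures. The Clopper-Pearson upper limit at a count of 0.31 × 15 = 4.65 is 59.4%, within the 60% target; at n = 14 it is 60.5%. Dropout: 20 / (1 − 0.20) = 25. Both reproduce. Following every case to 1 year leaves 25 unchanged, so this point concerns completeness and not sample size.

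**Which exits are by rule.**

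| Exit | Status |
|---|---|
| Nail removal | By rule (Protocol 7.2; exit reason in SAP 22) |
| Serious or intolerable AE | Possible, and only if it prevents continuation (8.3) |
| Lack of response, major protocol violation | Possible (8.3) |
| Selection criterion no longer met | Possible (8.3); covers active infection on one reading of 8.2 with 9.2.2 |

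**Effect on each endpoint.**

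1. *Primary.* It is a yes/no outcome per procedure, and the full analysis implant set (FAIS) holds all JTIN applications (Protocol 12.1.1, SAP 13). If 8 of 25 procedures have a related AE and some of them exit because of it, the result is still 8/25 = 32.0% (95% CI 14.9 to 53.5). What can be lost is a first related AE after an exit for some other reason. Each one is 1/25 = 4 points on 25 procedures, or 1/20 = 5 points on 20.
2. *Fracture-free survival.* SAP 24.3 counts procedures with a recorded fracture, so an exited case without one counts as fracture-free. For Kaplan-Meier, the SAP promises a number censored but defines time only from surgery to fracture. A case without a fracture has no defined time.
3. *Implant survival.* SAP 24.1 compares exit for nail removal with all other exit reasons. Assuming one reason is coded per case, a case coded to the AE reason counts as surviving even if the nail comes out then or later. Illustration: 4 of 20 nails removed gives 16/20 = 80% (95% CI 56.3 to 94.3). If 2 of those 4 carry another exit code, it reads 18/20 = 90% (68.3 to 98.8).
4. *AE detail.* Resolution, repeat events and later re-operations after exit are not collected.

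**Scale.** Protocol 11.1.6 gives literature surgical revision of 22.22% to 50%:

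- 25 × 0.2222 = 5.6 and 25 × 0.50 = 12.5 procedures.
- If all of these removed the nail, on average at mid-year (assumption), the follow-up lost is 0.2222 × 0.5 = 11% to 0.50 × 0.5 = 25% of planned time. If none did, removal costs nothing.

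**Crude fracture proportion, illustration.** Let p be the true 1-year risk, w the share exiting and t the exit time in years. Assume a constant hazard and exit unrelated to fracture:

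observed = (1 − w) × p + w × [1 − (1 − p)^t]

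Take p from the literature repeat-fracture range (11.11% to 37.29%, Protocol 11.1.6), w from 22.22% to 50%, and t from 0.25 to 0.75 (assumption).

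| True p | w = 50%, t = 0.25 | w = 22.22%, t = 0.75 |
|---|---|---|
| 11.1% | 7.0% | 10.5% |
| 37.3% | 24.2% | 35.6% |

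For example, 0.5 × 0.3729 + 0.5 × (1 − 0.6271^0.25) = 0.186 + 0.055 = 0.242 after rounding.

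**The case against.** The strongest reply is that little is lost. Four parts of it stand.

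- The 8.3 list gives possible reasons. A reader might infer that every serious AE, or every newly met exclusion criterion, ends follow-up. The text does not say so. The AE must prevent continuation, and 8.3 defines premature discontinuation by absence from the final visit. A child with a complication who attends that visit has not discontinued under that definition.
- A reader might also infer that deep infection is an exclusion criterion. It is not named as one. The link runs through contraindications worded for surgical candidates, so it is one reading of an unclear bullet.
- A related AE that triggers exit has already been counted in the primary endpoint. It might be inferred that replacement deletes such cases. If 5 of 8 affected cases were dropped as non-evaluable, 8/25 = 32.0% would become 3/20 = 15.0% (95% CI 3.2 to 37.9). The FAIS definition argues against this, although the protocol never defines evaluable.
- Removal is a natural end for device observation, since a case is one nail in one bone and later events may reflect the next device. Vigilance reporting also continues, but it does not feed the study dataset.

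The literature revision rates come from other devices, with no follow-up period stated in 11.1.6, so they show scale and do not measure bias.

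The reply leaves two things unanswered. Recording does stop at removal by rule, and nothing requires chart data to 1 year after any exit. The completion effort in 8.3 is worded for a patient's own decision to withdraw and does not clearly cover an exit made by the investigator.

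**Conclusion.** The point holds in a limited form. Only nail removal ends a case by rule; the other exits are permitted. The documents do not support a claim that the primary percentage loses the complications that cause exit. Its exposure is limited to first related AEs after an exit for another reason, at 4 points each on 25 procedures.

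The larger exposure is in the secondary endpoints and in AE outcome. The crude fracture proportion is biased towards fracture-free, implant survival can be overstated by exit coding, and later re-operations and resolution are missing. The overall size is not known. The figures of 5.6 to 12.5 procedures and 11% to 25% of follow-up time are upper illustrations that assume every revision removes the nail, the latter also mid-year removal; the lower bound from removal is zero. The fracture figures assume a constant hazard and exit unrelated to fracture. Under those assumptions a Kaplan-Meier estimate censored at exit would be unbiased. It would not be if exited children differ in risk, which is why the data themselves are needed.

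**What to change.** Separate the end of device observation from the end of data extraction. Clinical judgement and the family's right to object stay as they are.

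- **Protocol 7.2 and 8.3.** State that AEs, fracture, union, removal and re-operation of the treated bone are extracted from the chart to 1 year after index surgery, unless the family objects, the patient dies or is truly lost. State that an AE, lack of response, a protocol violation or a later change in a selection criterion does not by itself end extraction.
- **SAP 22.** Record nail removal (with its date) and the AE as event fields.
- **SAP 24.1.** Derive implant survival from the removal or exchange event. This must change together with SAP 22, because 24.1 now rests on the exit reason alone.
- **SAP 24.3.** State censoring at last chart contact for cases without a fracture.
- **Reporting.** Flag post-removal events and show results with and without them.
- **Consistency.** Reconcile the Synopsis, Protocol 7.2 and 8.3, and SAP 22, 24.1 and 24.3.

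The cost is an amendment with ethics notification, a check of the information sheet, eCRF and SAP edits, and chart entry for the cases that left early. No visit is added. The SAP cites an eCRF version of November 2024, so the change may come late. Retrospective extraction is already a study method, so records of children still in care can be completed.
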